4.1 Overview

The PharmText BP study was funded in September 2019 by the National Heart, Lung, and Blood Institute (NHLBI) of the National Institutes of Health (NIH). The study is being led by University of Iowa co-principal investigators [name], Associate Professor of Pharmacy Practice and Science and [name], [name] of Pharmacy Practice and Science and in the Department of Family Medicine.

The goal of PharmText BP is to conduct a study to evaluate whether our scalable SMS approach combined with a pharmacist-based intervention will improve BP management and that it will be cost effective. The entire study will last 5 years and involve recruitment of 420 participants from 3-4 clinics within 35 miles of University of Iowa Hospitals and Clinics. Participating clinics are listed in Appendix 1. All participants will live in areas that are considered rural by Rural-Urban Commuting Area Codes. The study aims to enroll at least 125 participants (30%) who represent minority populations.

All participants will have an initial screening/enrollment/baseline visit, a 2nd visit at 6 months, and a final visit at 12 months with a research intern. Each in-person visit will include research blood pressure measurements (Omron HEM 907-XL), interviews, and medical record review. In addition to the in-person visits, all participants will be provided with a home BP cuff (Omron 5 Series), enrolled in our bi-directional text-messaging platform, WyBP, and asked to submit 7 morning and 7 evening BP measurements via text message following the baseline visit. Text message prompts asking for these BP measurements will stop after the 14 measurements have been submitted, or after 15 days, whichever occurs first. Following the home BP measurements, participants will be randomized to either the pharmacist intervention arm or the texting-only control arm using a randomized block design with random block sizes with stratification according to clinic.

A timeline for the study procedures is provided in Appendix 2.

Key personnel roles for the study are described below:

Key Personnel	
Research Interns	3-5 full time staff members employed by Internal Medicine at UIHC who will recruit participants and collect data.

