Aim 1 Analysis: The analysis will be done on an intent-to-treat basis regardless of the number of reported BP readings or the number of pharmacist interactions with the participant. Our primary outcome will be a comparison of mean SBP values at 12 months. We will use linear mixed effects models (LMMs) with BP as the outcome. We will explore the timing of the change by also evaluating BP at 6 months. To test the intervention, we will include time (baseline, 6 month, 12 month) as a fixed effect factor and its interaction with treatment arm. We will use random effects for clinic and physician nested within clinic to account for practice heterogeneity between clinics and providers. Temporal correlation will be accounted for by using an autoregressive error structure. Specifically, the model will be given as

$$\begin{aligned}
 BP_{cpit} &= \tau_t + \alpha_c + \gamma_{cp} + (\omega_t + \nu_{tc} + \xi_{tcp})X_{cpi} + \epsilon_{cpit}, \\
 c &= 1, \dots, C, \quad p = 1, \dots, P_c, \quad i = 1, \dots, n_{cp}, \quad t \in \{0, 6, 12\}, \\
 (\alpha_c, \gamma_{cp})' &\stackrel{\text{iid}}{\sim} N(0, G_1), \\
 (\nu_{0c}, \nu_{6c}, \nu_{12c})' &\stackrel{\text{iid}}{\sim} N(0, G_2), \\
 (\xi_{0cp}, \xi_{6cp}, \xi_{12cp})' &\stackrel{\text{iid}}{\sim} N(0, G_3), \\
 (\epsilon_{cpio}, \epsilon_{cpis}, \epsilon_{cpis})' &\stackrel{\text{iid}}{\sim} N(0, R),
 \end{aligned}$$

where C is the number of clinics, P_c is the number of providers within the c^{th} clinic, n_{cp} is the number of subjects recruited under the p^{th} provider in the c^{th} clinic, $BP_{(cpit)}$ is the blood pressure at time t for the i^{th} subject under the p^{th} provider within clinic c , τ_t is the control mean at time t , α_c and γ_{cp} are the random control effects for the clinic and provider-nested-within-clinic respectively, ω_t is the treatment effect at time t , ν_{tc} and ξ_{tcp} are the random treatment effects for the clinic and provider-nested-within-clinic respectively, X_{cpi} equals 1 if the i^{th} subject under the p^{th} provider within clinic c is assigned to the treatment group and zero otherwise, ϵ_{cpit} is the (auto-correlated) noise term, and G_1 , G_2 , G_3 , and R are covariance matrices for the random effects. This model will also be estimated for DBP.

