Second, transition to control for patients who were uncontrolled at their baseline visit will be modeled using a generalized linear mixed effects model (GLMM) based on the Bernoulli distribution with a logistic link. We will test the intervention by including a fixed-effects term for the treatment assignment (intervention versus control). As before, we will include random effects for provider nested within clinic. Specifically, the model will be

$$\begin{aligned}
 \text{logit}(\mathbb{P}(Z_{cpio} = 1 | Z_{cpis} = 0)) &= \tau + \alpha_c + \gamma_{cp} + (\omega + \nu_c + \xi_{cp})X_{cpi}, \\
 (\alpha_c, \gamma_{cp})' &\stackrel{\text{iid}}{\sim} N(0, G_1), \\
 (\nu_c, \xi_{cp})' &\stackrel{\text{iid}}{\sim} N(0, G_2),
 \end{aligned}$$

where Z_{it} equals 1 if the i^{th} subject under the p^{th} provider within clinic c is controlled at time t , $t \in \{0, 6\}$, and zero otherwise.

Third, we will assess the duration of the change by modeling the odds of having controlled BP at 12 months among those uncontrolled at baseline but controlled at 6 months using a GLMM similar to that described above. All three models will contain any covariates (e.g., age, sex) that were not sufficiently addressed through randomization. In all analyses, the random effects incorporated into the final model will be chosen via Akaike Information Criterion with correction for small sample sizes (AICc).

Power: Based on prior work with the CAPTION trial, we expect a mean decrease in SBP of 17.3 (SD = 17.7) mmHg in the intervention arm and a decrease of 11.6 (SD = 18.2) mmHg in the control arm. We expect a difference of 5.65 mmHg between the groups with an expected pooled standard deviation of 17.9 with equal sized groups. In order to have 90% power to detect a difference of 5.7 mmHg or larger decrease in SBP with a Type I error rate of 5% and a standard deviation of 17.9 mmHg, we would need 180 subjects per arm or 360 subjects total.

In preliminary work in the CAPTION trial, 13.4% of control subjects dropped out or were lost to follow-up. 14.0% of subjects dropped out of the intervention arm during the first 9 months. In order to retain power after reasonable attrition rates over 12 months, we will recruit an additional 14% in each group to ensure we have at least 85% power. In addition, the sample size should be slightly increased to accommodate the interim analyses. This increases our total sample size to 420.

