Aim 3 Analysis: The analysis will be performed on an intent-to-treat basis regardless of the number of reported BP measurements or the number of pharmacist interactions with the subject. The perspective of this cost analysis is society in general. For each patient encounter, pharmacists will record the number of minutes spent in the following activities: medical record review, consultation, patient assessment, ordering medications, medical education, lifestyle education, BP measurement education, making recommendations, and documentation in the medical record. Pharmacist costs will be estimated by multiplying the time spent by their compensation rate. Costs for clinic visits will be obtained from the university. Utilization measures will be converted to costs per subject using the Medicare fee schedule for visits. Pharmacist and physician salaries will be obtained from the Bureau of Labor Statistics. The average wholesale drug cost for prescription medications will be obtained from Lexicomp Online (<https://online.lexi.com>). Generic prices will be used when available. The drug cost per prescription for each subject will be calculated by multiplying the average wholesale price (AWP) by frequency and dose.

We assume that subjects in the intervention and control groups will have similar characteristics. However, if there are significant differences between the subjects in these groups, costs will be predicted using a multivariate generalized linear model with a gamma family and a log link to control for these differences.

We will determine the cost of the intervention by subtracting the average total cost (pharmacist, clinic, and drugs) for the intervention group from the average total costs for the control group. The ICER is calculated as the cost differential from the intervention divided by the outcome differential from the intervention. Our primary outcome will be average decrease in SBP, and the outcome differential will be the average decrease in SBP for the control group minus the average decrease in SBP for the intervention group. The result of this analysis will be an ICER, which gives the additional cost of the intervention per mm Hg of SBP decrease.

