We will conduct at least two sensitivity analyses. Because the drug costs (average wholesale prices) from Lexicomp often overstate the actual prices paid by insurance companies and patients, we will adjust our drug costs and re-estimate our cost-effectiveness analysis. Specifically, the Kaiser Family Foundation estimates that average wholesale prices are, on average 17% higher than weighted acquisition costs for brand-name drugs, and 80% higher for generic drugs. In addition, pharmacist time can be represented by either wages per hour, or the

amount that pharmacists can bill Medicare for each activity. We will consider both ways to measure the value of pharmacists' time.

7. Data Safety and Monitoring

All procedures and protocols will be developed by the PIs and the study coordinator with protection of the participants and data as the highest priority. All procedures will be reviewed by the University of Iowa IRB as well as the Data and Safety Monitoring Board prior to being implemented (additional information about DSMB members and responsibilities can be found in the DSMB Charter). The study coordinator will thoroughly train and monitor all research interns during the course of the study and will be available to answer questions via phone when not in the clinic.

8. Study Responsibilities

By signing this protocol, the study's two PIs agree to be responsible for implementing and maintaining quality control and quality assurance systems to ensure that all work incidental to this protocol is conducted and data are generated, documented, and reported in compliance with the protocol, with accepted standards of Good Clinical Practice (GCP), and with all applicable federal, state, and local laws, rules, and regulations relating to the conduct of the clinical study.

Once the study activities are completed, the PIs will be primarily responsible for creation, review, and submission of publications and presentations relating to major aspects of the study and approved analyses within a timely fashion.

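### Aim 3 adjusts costs only if the arms differ significantly, so the data rather than the plan decide which cost estimate enters the ICER

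*Combined protocol and SAP*

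**What the plan says.** The cost rule is in Section 6 (Statistical Design and Power), Aim 3 Analysis. It starts from an assumption of balance: "We assume that subjects in the intervention and control groups will have similar characteristics". The default contrast is a raw difference in means: "We will determine the cost of the intervention by subtracting the average total cost (pharmacist, clinic, and drugs) for the intervention group" from the control group's. The exception follows from the balance assumption: "if there are significant differences between the subjects in these groups, costs will be predicted using a multivariate generalized linear model", using a gamma distribution and log link. The plan then names its checks: "We will conduct at least two sensitivity analyses". The two it describes concern drug prices and the valuation of pharmacist time. Neither compares adjusted with unadjusted costs.

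The Aim 1 Analysis in the same section has a looser rule for blood pressure: "All three models will contain any covariates (e.g., age, sex) that were not sufficiently addressed through randomization". Baseline blood pressure falls outside that rule, because it is one of the modelled time points: "we will include time (baseline, 6 month, 12 month) as a fixed effect factor and its interaction with treatment arm".

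Allocation is described in Section 4.1 as "using a randomized block design with random block sizes with stratification according to clinic". Section 5 makes the ICER the main outcome of Aim 3, while cost is a secondary outcome of the trial as a whole.

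**The concern.** If allocation is sound, differences between the arms at baseline arise by chance. A p-value for such a difference reflects the size of the imbalance relative to chance. It does not show whether the variable predicts cost. A rule keyed to significance can adjust for variables that do not matter and omit strong predictors that happen to be balanced, although adjusting for a strong predictor improves precision even when it is balanced.

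The rule also leaves the Aim 3 estimate undefined until the data are seen. Depending on the trigger, the ICER numerator is either a raw difference or a model prediction. The plan does not say which variables are tested, at what level or when, how predicted costs enter the ratio, or which result is the reported one if both are produced. The trigger concerns costs only, so an adjusted cost could end up divided by an unadjusted SBP effect.

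**Working it through.** The plan states no figure for the trigger, so there is none to reproduce. The calculations below show how often it might fire and what follows.

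**Inputs from the documents.** The synopsis gives 180 evaluable per arm, a difference of 5.7 mmHg, SD 17.9, 5% type I error and 85% power. These reproduce: the two-sample formula gives 178 per arm, and power at 180 is 0.856. (Section 6 states 90% for the same 180. That is a separate matter and is not used here.) Appendix 5 offers 18 comorbidities, 6 demographic items, 8 tobacco items and 2 alcohol items: 18 + 6 + 8 + 2 = 34. Counting only the two tobacco status items gives 18 + 6 + 2 + 2 = 28.

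**Assumptions.** Significant means two-sided p<0.05 for each variable. The correlations and cost slopes below are illustrative.

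**Chance that at least one variable triggers adjustment under sound randomisation.** For k independent variables this is 1 − 0.95^k. For correlated variables, equicorrelated normal test statistics were simulated (200,000 draws).

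| k | Independent | Correlation 0.2 | Correlation 0.4 |
|---|---|---|---|
| 10 | 1 − 0.599 = 0.401 | 0.376 | 0.321 |
| 20 | 1 − 0.358 = 0.642 | 0.590 | 0.483 |
| 30 | 1 − 0.215 = 0.785 | 0.723 | 0.590 |

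**Effect on a test of a continuous outcome.** The simulation used 180 per arm, an effect of 5.7/17.9 = 0.318 SD, one covariate with correlation r to the outcome, and t-test against ANCOVA. There were 20,000 replicates under the null and 10,000 under the alternative.

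| | r = 0.3 | r = 0.5 | r = 0.7 |
|---|---|---|---|
| Type I error, always adjust | 0.053 | 0.049 | 0.052 |
| Type I error, test then adjust | 0.050 | 0.043 | 0.038 |
| Power, always adjust | 0.88 | 0.93 | 0.99 |
| Power, test then adjust | 0.86 | 0.86 | 0.87 |

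Test-then-adjust does not inflate type I error, but it forgoes most of the power that adjustment offers. This is a simple two-group comparison with one covariate, not the planned mixed model. It shows the direction of the loss rather than a forecast for this trial.

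**Effect on a cost difference.** The simulation used gamma costs (shape 2), a treatment log-effect of 0.2, one covariate with a log-mean slope of 0.2 or 0.4 per SD, 180 per arm and 1,500 replicates. When the trigger fired, the raw and the standardised adjusted differences were apart by an average of 26% (slope 0.2) or 50% (slope 0.4) of the cost difference. When it did not fire, they were still apart by 10% or 21%. So the choice of analysis can visibly move the ICER numerator, and an insignificant imbalance does not make the two analyses agree.

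**The case against.** Several points on the other side are sound.

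- A reader might infer that the primary SBP analysis also hangs on a significance test. The text does not support that. Aim 1 mentions no test, and since allocation is stratified by clinic only, its wording can be read as adjusting for factors the design did not balance. Baseline blood pressure is in that model in any case. What stands is that the wording lists no covariates and leaves the choice until imbalance has been seen.
- A reader might infer inflated false positives or misleading confidence intervals. A fixed rule does not inflate type I error in the simulation, and the plan describes no interval or test for costs or the ICER. Error rates of 0.067, 0.073 and 0.085 (r = 0.3, 0.5, 0.7) arise only if the more favourable of two analyses may be reported, and the plan does not say that it may.
- The trigger probabilities rest on an unstated 5% level. The independent figures are also too high for a form with related items, such as angina, coronary disease and MI. Hence the range.
- Aim 3 speaks of differences between the subjects without limiting them to baseline. Participants analysed at 12 months could differ through dropout, planned at about 14%, which need not be chance. That is a reason to adjust for known predictors regardless. It is not a reason to select them by p-value.
- The fallback model's form is named in advance, so it is not invented after costs are seen. Its covariates, however, are not named.

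**Conclusion.** The point holds for Aim 3 as written: adjustment of costs depends on significance between randomised groups, and nothing elsewhere in the documents fixes a covariate set or says which estimate enters the ICER. The consequences are an estimate that depends on the data, lost precision, and possible omission of balanced but strong predictors.

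At an assumed 5% level and 10 to 30 variables, the chance of switching is about 40% to 79% if they are independent, or 32% to 59% at correlation 0.4. These percentages should not be read as the size of a bias. For Aim 1 the finding is narrower: a vague imbalance rule that should be replaced by a list. The change is worth making, but the documents give no ground for calling the primary comparison invalid.

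**What to change.** **Aim 3.**
- Delete the significance trigger.
- Always fit the gamma log-link cost model with covariates fixed before unblinded data are seen, all already collected: clinic, baseline SBP, age, sex, insurance type and number of baseline blood pressure drugs.
- Report the standardised mean cost difference: predict each participant's cost under both arms, average, and subtract.
- In the ICER denominator, use an SBP difference adjusted for the same covariates, for example from a regression of the 12-month decrease on arm and this list.
- Label the unadjusted ICER a sensitivity analysis.

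**Aim 1.** Replace the imbalance wording with a fixed list (age, sex, insurance type, number of baseline blood pressure drugs), included whatever the observed balance. Do not add baseline SBP or fixed clinic terms to the longitudinal model: baseline blood pressure is already a response there and clinic already a random effect.

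**Cost.** SAP wording only. The cost model spends roughly 9 to 11 degrees of freedom (clinic 2 to 3, insurance 3, sex 1 to 2, and one each for age, baseline SBP and drug count) against about 360 evaluable participants. It also relies on the gamma log-link form, which the unadjusted sensitivity analysis checks.

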2.2 Aims and Hypotheses

2.2.1 Aim 1: Determine if our intervention leads to decreases in BP.

2.2.1.1 Hypothesis: Mean systolic BP in the pharmacist-intervention group will be significantly lower than mean systolic BP in the control group at 6 and 12 months.

2.2.1.2 Hypothesis: Mean diastolic BP in the pharmacist-intervention group will be significantly lower than mean diastolic BP in the control group at 6 and 12 months.

2.2.2 Aim 2: Determine if our intervention leads to intensification of therapy.

2.2.2.1 Hypothesis: Participants in the pharmacist-intervention group will have more treatment changes, on average, than those in the control group.

2.2.3 Aim 3: Determine the cost effectiveness of the intervention.

2.2.3.1 Hypothesis: The intervention will be cost effective when compared to the control group.

3. Subject Inclusion/Exclusion Criteria

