Our working hypothesis is that there will be a greater number of medication changes in the intervention group compared to the control group. We will count the number of medication changes (dose increased, dose decreased, drug stopped, drug started) during the 12 months following the start of the intervention. The total number of medication changes will be the primary outcome measure for Aim 2. In addition, we will determine the number of pharmacist recommendations that were accepted by physicians. These are process measures: we found in our previous studies that BP improvement was primarily related to medication changes. We are assuming that changes are a sign of close monitoring. Indeed, we have used this measure previously. However, we realize that not all medication changes are equal, and thus we will record both medication trends and final treatment for each patient.

Aim 3: Determine the cost effectiveness of the intervention.

Our working hypothesis is that our intervention will be cost effective when compared to the control group. In addition, we will compare these results to previous pharmacist interventions. Because much pharmacist time is spent on non-direct patient care activities, we are convinced that our bi-directional texting approach will be both labor and cost saving. We will compute the incremental cost effectiveness ratio (ICER) using the total costs of doctor visits, pharmacist time, medications and medication changes during the 12 months of the trial. The ICER will be the difference between the control and intervention groups in average total cost

divided by the difference in average decrease of SBP and DBP. The ICER will be expressed in the dollars per mmHg reduction in BP and will be the primary outcome in this Aim.

6. Statistical Design and Power

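### Aim 3 hypothesises cost effectiveness, but its planned result is a point-estimate ICER: sampling uncertainty is not carried through, and nothing says how to judge a costlier, more effective result

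*Combined protocol and SAP*

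**What the plan says.** Section 2.2 gives Aim 3 a directional hypothesis: "The intervention will be cost effective when compared to the control group". Section 5 names the measure for that aim: "The ICER will be expressed in the dollars per mmHg reduction in BP and will be the primary outcome in this Aim".

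Section 6 (Aim 3 Analysis) defines the estimator, "The ICER is calculated as the cost differential from the intervention divided by the outcome differential from the intervention", and then the end product: "The result of this analysis will be an ICER, which gives the additional cost of the intervention per mm Hg of SBP decrease".

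Three other statements bear on uncertainty or on a benchmark:

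- Section 6: "We will conduct at least two sensitivity analyses". Two are described. One lowers the average wholesale drug prices. The other values pharmacist time by hourly wage or by what can be billed to Medicare.
- Section 6: if the groups turn out to differ significantly in their characteristics, "costs will be predicted using a multivariate generalized linear model with a gamma family and a log link to control for these differences".
- Section 5: "In addition, we will compare these results to previous pharmacist interventions". No figure or rule is attached.

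**The concern.** The hypothesis calls for a judgement, and the analysis supplies one number. Aims 1 and 2 each have a model for the treatment effect, a Type I error rate and a power statement. The Aim 3 text has no interval, resampling scheme, net-benefit analysis or test, and no value per mmHg.

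A ratio of two estimated differences is a poor basis for judgement when given alone. It is sensitive to error in its denominator. Its sign is also ambiguous: a negative ICER can mean cheaper and better, or dearer and worse.

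At stake is how the Aim 3 statement is reached. If the intervention costs more and lowers SBP more, whether it is cost effective depends on what a mmHg is held to be worth. If that value is chosen after the ICER is known, the conclusion carries little weight.

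**Working it through.** **1. Inputs.** From the synopsis and Section 6 (Power): SBP falls by 17.3 (SD 17.7) mmHg with the intervention and by 11.6 (SD 18.2) among controls. The planning assumption reads: "We expect a difference of 5.65 mmHg between the groups with an expected pooled standard deviation of 17.9 with equal sized groups". The difference to detect is 5.7 mmHg, and 180 per arm are evaluable. Aim 3 has no expected cost difference, cost SD or cost-effect correlation.

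**2. The plan's own figure.** n per arm = 2(1.96 + 1.036)² × 17.9² / 5.7² = 177.1, so 178 (181 at 5.65 mmHg). With 180 per arm, power at 5.7 mmHg is 0.856. The stated 180 therefore reproduces at the synopsis's 85% power. Section 6 attaches 90% to the same 180, which would need 208 per arm; that is a separate point.

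**3. Sampling error of the ICER denominator.**

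- SE = 17.9 × √(2/180) = 1.89 mmHg.
- 95% interval = 5.7 ± 1.96 × 1.89 = 2.0 to 9.4 mmHg.

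**4. Effect on the ICER, cost difference held fixed.** The ICER is then proportional to 1/(SBP difference).

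- Lower multiple: 5.7/9.4 = 0.61.
- Upper multiple: 5.7/2.0 = 2.85.
- Ratio of the two ends: 9.4/2.0 = 4.7.

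| Inputs | SE | 95% interval (mmHg) | ICER multiple |
|---|---|---|---|
| 5.7, SD 17.9, 180 per arm | 1.89 | 2.0 to 9.4 | 0.61 to 2.85 |
| 5.65, arm-specific SDs, 180 per arm | 1.89 | 1.94 to 9.36 | 0.60 to 2.91 |
| 5.65, arm-specific SDs, 210 per arm (no dropout) | 1.75 | 2.22 to 9.08 | 0.62 to 2.55 |

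**5. Adding cost variability (assumed costs, zero correlation).** With E and C the SBP and cost differences, the Fieller limits are the roots R of (E² − 1.96²SE_E²)R² − 2ECR + (C² − 1.96²SE_C²) = 0. Here E = 5.65, SE_E = 1.89 and SE_C = (cost SD) × √(2/180).

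| Assumed cost difference | ICER per mmHg | SD $0 | SD $500 | SD $1000 | SD $2000 |
|---|---|---|---|---|---|
| $200 | $35 | $21 to 103 | $15 to 110 | −$1 to 126 | −$43 to 167 |
| $400 | $71 | $43 to 206 | $39 to 210 | $29 to 219 | −$2 to 251 |

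The variance of C − R·E contains −2R·cov(C, E). For positive R, a positive correlation between cost and SBP reduction therefore narrows these intervals, and a negative one widens them.

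**6. Dependence on the value of a mmHg.** Net monetary benefit at λ dollars per mmHg is λE − C. With $400 and SD $1000, λ = $100 gives 565 − 400 = 165. Its SE is √[(100 × 1.892)² + 105.4²] = 216.6, so the probability that it exceeds zero is Φ(0.76) = 0.78. The same calculation gives 0.20 at $50, 0.55 at $75 and 0.93 at $150.

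Steps 5 and 6 show the mechanism only. Their dollar figures are assumptions and say nothing about this trial's likely costs.

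**The case against.** **No threshold is needed if the intervention is cheaper and better.** This stands. A reader might infer that the plan can neither support nor refute its hypothesis, and that goes too far. Section 5 expects the texting approach to save labor and cost, and lower cost with lower SBP would settle the matter without a value per mmHg. Section 5 does not say what the saving is measured against, however, and Section 6 speaks of an additional cost. A dominance claim would also need its sampling uncertainty stated.

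**The plan prescribes no verdict from the point value.** This also stands. A reader might infer that the trial will declare cost effectiveness from the bare ICER, but no section says so. The fault is a missing link between hypothesis and analysis.

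**Uncertainty is partly covered elsewhere.** The Aim 1 mixed model will yield uncertainty for the SBP effect, and the list of sensitivity analyses is open-ended. The first covers the denominator only. The second commits to nothing about sampling error. The gamma model is conditional on imbalance, concerns costs only and is not linked to an interval for the ICER.

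**A benchmark exists.** Earlier pharmacist interventions are a legitimate comparator. A previous ICER is not a statement of what a mmHg is worth, so it cannot serve as the threshold. I could not read Section 1.2 (clinical experience with the intervention) and cannot exclude that it quotes a prior cost result. It would still be a comparator.

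**The range is illustrative.** Agreed. The 4.7-fold figure might be read as a minimum, but it holds cost fixed, and positive cost-effect correlation could narrow the interval.

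**Conclusion.** The point holds as a gap in the Aim 3 analysis. A directional hypothesis is paired with a point ICER and with price and valuation sensitivity analyses, so joint sampling uncertainty in cost and SBP does not reach the conclusion. The plan also does not say how to judge a result that is both costlier and more effective. The missing threshold alone would be a matter of detail. The stronger ground for change is that a better analysis is available from data already being collected.

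On size, SBP sampling error alone gives 0.61 to 2.85 times the point ICER. This assumes the plan's 5.7 mmHg and SD of 17.9, 180 evaluable per arm, independent participants and a fixed cost difference. The actual range depends on cost variability and correlation, which the documents do not give.

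Cost is a secondary outcome, and the primary SBP comparison is untouched. This is a cheap improvement worth making before the data are analysed.

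**What to change.** Add one paragraph to the Aim 3 Analysis in Section 6:

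1. Resample participants within arm and clinic, keeping each person's total cost and SBP change together. Check sensitivity to physician-within-clinic clustering, which Aims 1 and 2 model.
2. Handle missing 12-month SBP consistently with Aim 1, for example by refitting that model in each resample. The sample size allows for 14% attrition, so complete cost-SBP pairs should not be assumed.
3. Report the cost difference, the SBP difference and net monetary benefit with 95% intervals, and an acceptability curve over a dollars-per-mmHg range fixed before the data are seen. The ICER can stay as a descriptive summary.
4. Base the Aim 3 statement on these results, and say how they will be read if the intervention costs more and lowers SBP more. Repeat the drug-price and pharmacist-time analyses on the same footing.
5. Present earlier pharmacist-intervention results as a comparator, not as the threshold.

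If the sponsor does not wish to fix a range, the simpler course is to reword Aim 3 as estimation and report an interval.

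The cost is a short program and a few sentences of plan text, with no new data collection. The downside is that the conclusion may be less clear-cut.
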